**Study Endpoints:**

The primary outcome is clinical benefit at 90 days defined as a composite of all cause mortality, number of heart failure events (including hospitalization for HFs, urgent heart failure visits and unplanned outpatient visits), time to first heart failure event and change in KCCQ-TSS from baseline.

Secondary outcomes include improvement in KCCQ-TSS of  $\geq 10$  points after 90 days of treatment, change from baseline in log-transformed NT-proBNP levels over 90 days, days alive and out of hospital until 90 days, time to first occurrence of CV death or HFE until end of trial period, and change in 6-minute walk test and change in KCCQ-TSS between baseline and 90 days. Secondary safety endpoints include Occurrence of chronic dialysis or renal transplant or sustained reduction of  $\geq 40\%$  eGFR, or Sustained eGFR  $< 15\text{mL/min}/1.73\text{m}^2$  for patients with baseline eGFR  $\geq 30\text{mL/min}/1.73\text{m}^2$ , or Sustained eGFR  $< 10\text{mL/min}/1.73\text{m}^2$  for patients with baseline eGFR  $< 30\text{mL/min}/1.73\text{m}^2$ .

**Statistical analysis:** Categorical variables will be reported as percentages and counts, and continuous variables will be reported as means  $\pm$  standard deviations. Data analysis will be performed using STATA version 15 software (College Station, TX, USA).

Cost-effectiveness analysis will be performed to calculate incremental-cost effective ratio (ICER) for HFE avoided and QALY gained. Events of patients enrolled in the registry will be used as reference comparator. Costs will be based on Hospital Authority gazette prices for hospital admissions and visits.

*Table 1. Data to be collected in this study*

	Enrollment	30 days	60 days	90 days
Patient Informed Consent	x			
History including baseline characteristics	x			
Baseline co-morbidities:	x			

Baseline and in-hospital medications	x			
Physical examination include body weight	x	x	x	x
Laboratory test including NT-proBNP or BNP within 72hr of index admission, eGFR	x	x	x	x
Clinical events: all cause mortality, cardiovascular-associated death, A&E visit for acute heart failure, unplanned outpatient clinic visit, re-admission for heart failure	x	x	x	x
6MWD	x			x
Symptoms QOL assessment: NYHA class, KCCQ-TSS	x			x
Prescription records of SGLT2 inhibitors	x	x	x	x
Adverse drug effects	x	x	x	x

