**Draft Protocol v.1.2**

**Principle Investigator:** [name] [name] (CUHK)

**Co-Investigator:** [name], [name], [name], [name], [name], [name], [name]

Protocol Summary	
Design:	Prospective, single-centre, non-randomized, open-label
Target Enrolment:	100 subjects
Study drug:	Empagliflozin 10mg oral tablet daily
Study location	The Chinese University of Hong Kong/ Prince of Wales Hospital.
Study duration	90 days
Inclusion Criteria	

1. Subject age >18 hospitalized for primary diagnosis of acute HF

2. Dyspnoea (exertional or at rest) and 2 of the following signs:

- Congestion on chest X-ray

- Rales on chest auscultation

- Clinically relevant oedema (e.g. <math>\geq 1+</math> on a 0 to 3+ scale)

- Elevated jugular venous pressure

3. Stabilization criteria (while in the hospital):

- SBP <math>\geq 100</math> mmHg and no symptoms of hypotension in preceding 24 hours

- No increase in i.v. diuretic dose for 24 h prior

- No i.v. vasodilators including nitrates within the last 6 h prior

- No i.v. inotropic drugs for 24 h prior

4. NT-proBNP <math>\geq 1600</math> pg/mL or BNP <math>\geq 400</math> pg/mL. Patients with AF: NT-proBNP <math>\geq 2400</math> pg/mL or BNP <math>\geq 600</math> pg/mL. Measured during index hospitalization

5. Heart failure hospitalization that requires the treatment of a minimum single dose of 40 mg of i.v. furosemide (or equivalent i.v. loop diuretics defined as 20 mg of torsemide or 1mg of bumetanide)

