Exclusion Criteria	

1. Cardiogenic shock

2. Documented history of HF with previous HF admission

3. Current hospitalization for acute HF primarily triggered by pulmonary embolism, cerebrovascular accident, or acute MI

4. Interventions in past 30 days prior or planned during the study:

- Major cardiac surgery, or Tran Aortic Valve Implantation, or Percutaneous Coronary Intervention, or MitraClip

- Implantation of cardiac resynchronization therapy device

- Cardiac mechanical support implantation

4. Current or expected heart transplant, LVAD, IABP, or patients with planned inotropic support in an outpatient setting

5. Haemodynamically severe uncorrected primary cardiac valvular disease planned for surgery or intervention during the course of the study.

6. eGFR <math>< 20</math> mL/min/1.73m^2 as measured during index hospitalization (latest measurement before randomization) or patients requiring dialysis

7. Type 1 diabetes mellitus

8. History of ketoacidosis, including diabetic ketoacidosis

	9. Current or prior treatment with SGLT2 inhibitors in 90 days prior to enrolment
Primary Clinical Outcome	Clinical benefit, a composite of all cause mortality, number of heart failure events (including hospitalization for HFs, urgent heart failure visits and unplanned outpatient visits), time to first heart failure event, change from baseline in 6-minute walk distance (6MWD) and change from baseline in KCCQ-TSS after 90 days of treatment.

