The EMPULSE study which was recently presented at the 2021 American Heart Association Annual scientific session, demonstrated in-hospital initiation of empagliflozin in patients with acute heart failure regardless of left ventricular ejection fraction (LVEF) to be safe and effective (10). In this trial, 530 patients with acute HF were randomized 1:1 to 10 mg of empagliflozin or placebo once stabilized in the hospital (median 3 days) and followed-up for 90 days for the primary composite endpoint of time to death, frequency of HF events, time to first HF event, and change in quality of life score from baseline. About one-third (33%) patients randomized had new-onset acute HF, two-thirds (69.1%) of patients had LVEFs <40%, and 29% randomized to empagliflozin and 35% of those randomized to placebo had LVEF >40%. In terms of safety, rates of serious adverse events and any adverse events were both higher in the placebo arm. Acute renal failure, occurred in 7.7% of patients in the SGLT2 inhibitor arm compared with 12.1% of placebo-treated patients. For the primary composite endpoint, patients treated with empagliflozin were 36% more likely to experience a clinical benefit in the first 90 days (stratified win ratio 1.36; 95% CI 1.09-1.68). all-cause mortality (4.2% vs 8.3%) and heart failure events (10.6% vs 14.7%) were numerically lower in the empagliflozin arm. Improvement in quality of life was a key driver of difference in the primary endpoint: placebo-adjusted mean difference at 90 days was 4.5 points favouring empagliflozin. Other larger trials of treatment with SGLT2 inhibitor in acute heart HF are underway, including the DICTATE-AHF and DAPA ACT HF-TIMI 68 trials, both with dapagliflozin.

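### The primary clinical benefit composite has no combining rule, component order or named comparator, and the stated descriptive analysis cannot give it a value

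*Protocol*

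**What the plan says.** The Study Endpoints paragraph in section 2 (Methods) reads: "The primary outcome is clinical benefit at 90 days defined as a composite of all cause mortality, number of heart failure events". It then completes the list with "time to first heart failure event and change in KCCQ-TSS from baseline". That makes four components.

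The Primary Clinical Outcome row of the Protocol Summary has five. Its list ends: "time to first heart failure event, change from baseline in 6-minute walk distance (6MWD) and change from baseline in KCCQ-TSS after 90 days of treatment".

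The Introduction describes the apparent source, a trial in which "530 patients with acute HF were randomized 1:1 to 10 mg of empagliflozin or placebo", with a "primary composite endpoint of time to death, frequency of HF events, time to first HF event, and change in quality of life score from baseline". Its result is given as "stratified win ratio 1.36; 95% CI 1.09-1.68".

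The present study is "Prospective, single-centre, non-randomized, open-label". For the clinical data, the Statistical analysis paragraph says: "Categorical variables will be reported as percentages and counts", with means and standard deviations for continuous variables. It then turns to cost-effectiveness, and there it names the registry patients' events as the reference comparator.

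The registry itself is set up under Study procedure. It consists of eligible patients who declined the drug, followed as a reference group on the same assessment schedule.

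**The concern.** A death, an event count, a time and a change in score have no common unit. They become one outcome only through a rule. The rule may score each patient, define who counts as having benefited, or compare patients in pairs down a ranked list. The cited trial used the pairwise route, which needs two groups and an order. The protocol keeps the components and states none of these rules.

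If the protocol is followed as written, the trial yields a table of components and no primary result. Treatment is open-label, so if the rule is not fixed in advance it could be chosen with outcomes in view. Different rules can favour different groups.

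**Working it through.** **1. Can the stated analysis be applied?** A percentage with a count needs a category for each patient, and the protocol does not say which patient has clinical benefit. A mean with SD needs one number for each patient, and no score is defined. Neither summary applies to the composite. Each component can still be summarised separately.

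**2. Can a win ratio be formed?** The number of pairs is treated patients × comparator patients. With the treated group alone this is 100 × 0 = 0, so the ratio is undefined. With an assumed 50 registry patients it is 100 × 50 = 5,000, and the ratio exists once an order is fixed. The order matters. Take a survivor with one HF event and a large KCCQ-TSS gain, paired with a survivor with no event and a small gain. The first loses if events rank above KCCQ-TSS and wins if KCCQ-TSS ranks above events.

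**3. Is the component list settled?**

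| Component | Protocol Summary | Study Endpoints | Cited trial (Introduction) |
|---|---|---|---|
| Death | yes | yes | yes |
| Number of HF events | yes | yes | yes |
| Time to first HF event | yes | yes | yes |
| 6MWD change | yes | no | no |
| Quality-of-life change | KCCQ-TSS | KCCQ-TSS | yes |

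The two definitions in the protocol conflict on 6MWD.

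**4. Are the data collected?** Table 1 lists deaths and HF events at every visit, and KCCQ-TSS and 6MWD at enrolment and day 90. Study procedure applies the same assessments to the registry. The inputs for treated-by-registry pairs are therefore planned.

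**5. How precise would the registry comparison be?** The protocol states no power, effect size or sample-size derivation, so there is no figure of its own to reproduce. I scaled from the cited trial.

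- Log standard error from its CI: (ln 1.68 − ln 1.09) / (2 × 1.96) = 0.4326 / 3.92 = 0.110.
- Consistency: √(1.09 × 1.68) = 1.353, close to the stated 1.36; z = ln 1.36 / 0.110 = 2.79.
- Scaling to n treated and m registry patients: SE = 0.110 × √[(530 × 0.25) / (n·m/(n + m))].
- Example, n = 100 and m = 50: n·m/(n + m) = 33.3; SE = 0.110 × √(132.5 / 33.3) = 0.220; CI = 1.36 × exp(±1.96 × 0.220) = 0.88 to 2.09.
- Power = Φ(ln 1.36 / SE − 1.96), with two-sided alpha 0.05 assumed.

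| Treated | Registry (assumed) | Pairs | SE | 95% CI around 1.36 | Power |
|---|---|---|---|---|---|
| 100 | 25 | 2,500 | 0.284 | 0.78–2.37 | 19% |
| 100 | 50 | 5,000 | 0.220 | 0.88–2.09 | 29% |
| 100 | 100 | 10,000 | 0.180 | 0.96–1.93 | 40% |
| 200 | 50 | 10,000 | 0.201 | 0.92–2.02 | 33% |
| 200 | 100 | 20,000 | 0.156 | 1.00–1.85 | 51% |
| 200 | 200 | 40,000 | 0.127 | 1.06–1.75 | 68% |

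The treated numbers come from the Protocol Summary (100) and the Methods (up to 200). The Methods do not say whether 200 includes registry patients, so the last three rows assume that all 200 are treated.

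**The case against.** The strongest reply is that the study is not confined to one group. The design line says non-randomised and open-label, not single-arm. The registry is called a reference group, without limiting that role to costs where it is introduced. The Study Endpoints list follows the sequence of the cited trial, so the intended construct can be recognised. Ranking rules, tie handling and estimation are often left to an SAP, which may exist and is not shown. The statistics paragraph is general reporting language and does not claim to be exhaustive.

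Much of this stands. A reader might infer that no primary result can be produced in this design at all. The documents do not support that: the registry and Table 1 supply what a hierarchical comparison needs. Nor do they show that a combining rule would in fact be chosen after the data are seen, since an SAP could fix it beforehand.

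It does not remove the point. The defect lies in the endpoint that the protocol itself fixes. A recognisable sequence is not a stated hierarchy. The one place that gives the registry an analytic role covers events for cost-effectiveness, which leaves out KCCQ-TSS change. The conflict over 6MWD is between two definitions in the same document.

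**Conclusion.** The point holds. The primary outcome is not defined as an analysable quantity, it has no assigned comparator, and its component list is stated in two conflicting ways. This affects the whole primary result and should be corrected before the analysis is fixed. It is a gap in definition, not an impossibility: once the registry is named and an order is set, a result can be computed.

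That result would be non-randomised, because the comparison patients chose to decline the drug. It would probably also be imprecise, with about 19% to 40% power for 100 treated patients and 33% to 68% for 200, over the registry sizes assumed above. These figures rest on the cited effect carrying over, the cited standard error scaling with group sizes, two-sided alpha of 0.05 and no adjustment for confounding. They also take the cited composite, which has no 6MWD. They describe what the repaired analysis could show and do not measure the flaw itself.

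**What to change.** 1. Reconcile the component list in the Protocol Summary and in Study Endpoints, stating whether 6MWD change belongs to the primary outcome.
2. State that the primary outcome is analysed as a hierarchical win ratio of treated versus registry patients, with a 95% CI, in a fixed order: death, number of HF events, time to first HF event, then the change score or scores retained. If both scores stay, give their order.
3. Label the result non-randomised and exploratory, because the registry patients are self-selected decliners.
4. Report each component by group.
5. Optionally, add a supportive per-patient percentage with an exact 95% CI: alive, no HF event, and KCCQ-TSS improved by at least the 10 points already used in the secondary outcomes. By 1.96 × √(0.25/n), its half-width is at most about 9.8 points for 100 treated patients, or 6.9 if 200 are treated. It discards event frequency and timing and leaves out 6MWD, so it should not be required as a replacement.

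The cost is a paragraph of protocol wording and no new data collection. The downside is small: the primary result is openly non-randomised, and its precision depends on a registry size that the protocol does not state. An expected registry size should be added.

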Current guidelines recommend in-hospital echocardiogram in the clinical setting of new-onset or decompensated (6). However, echocardiogram is often delayed months after discharge or not performed at all under Hong Kong public hospital setting. As a result, initiation of guideline recommended therapies like ARB/ARNI/MRA/BB may be delayed for HFrEF patients awaiting echocardiogram or unnecessary for HFpEF patients. Out of the 4 guidelines recommended treatment for HF, only empagliflozin has proven benefits for the treatment of both HFrEF and HFpEF. Given that empagliflozin is well tolerated and its benefits are seen early, it may be reasonable to initiate empagliflozin early during index hospitalization even before the assessment of LVEF is available. However, costs remains a major barrier for early initiation of SGLT2-inhibitor.

The timing of SGLT inhibitors initiation in the treatment of acute HF is not established. In particular, new-onset acute HF is a group which is understudied in the major trials to date. This study aims to evaluate the efficacy and safety of in-hospital initiation of empagliflozin in patients hospitalized for new onset acute HF, regardless of LVEF for up to 90 days of follow-up.

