## 2. Methods

**Study design:** This is an investigator-initiated, prospective, single-centre, non-randomized open label study that evaluates the efficacy and safety of initiating empagliflozin during index hospitalization for acute heart failure regardless of LVEF.

**Patient population:** The study will recruit up to 200 patients.

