**Study procedure:**

Patients who meet inclusion and none of the exclusion criteria will be enrolled during hospitalization after stabilization. Patients should receive usual care per current relevant local and regional guidelines, as defined by their clinicians. Patients can be enrolled regardless of T2D status or ejection fraction. Enrolment is stratified according to patients with new-onset HF and worsening chronic HF. Informed consent will be signed before study enrolment. Baseline KCCQ-TSS and baseline 6MWT will be performed prior to study drug initiation and repeated at 30 and 90 days. Echocardiogram is not mandatory but permitted before subjects enrolment. Follow-up will be at 30 days, 60 days and 90 days.

Study drug will be dispensed by the research pharmacy provided by the study team (free of charge to the patient) as an open-label treatment.

Patients who meet inclusion and none of the exclusion criteria but declined study medication will be invited to be followed-up in a registry as reference group. These patients will follow the same baseline and follow-up assessment protocol (minus the study drug).

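### KCCQ-TSS and 6MWD endpoints are within-patient changes from an in-hospital baseline with no comparator named, so the treated group's change cannot be read as efficacy

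*Protocol*

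**What the plan says.** The Introduction states the aim: "This study aims to evaluate the efficacy and safety of in-hospital initiation of empagliflozin in patients hospitalized for new onset acute HF". Methods, Study design, describes a "prospective, single-centre, non-randomized open label study that evaluates the efficacy and safety of initiating empagliflozin during index hospitalization".

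Under Study procedure, patients "will be enrolled during hospitalization after stabilization", and "Baseline KCCQ-TSS and baseline 6MWT will be performed prior to study drug initiation and repeated at 30 and 90 days". Treatment of the admission continues alongside: "Patients should receive usual care per current relevant local and regional guidelines, as defined by their clinicians".

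Study Endpoints then lists the responder endpoint, "Secondary outcomes include improvement in KCCQ-TSS of $\geq 10$ points after 90 days of treatment", together with change in 6-minute walk and in KCCQ-TSS from baseline to day 90. Change in KCCQ-TSS is also a component of the primary composite. The version of the composite in the Protocol Summary adds change in 6MWD.

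Study procedure provides a reference group of eligible patients who decline the drug, followed in a registry on the same assessment schedule. Statistical analysis promises only counts, percentages, means and standard deviations. It names the registry as comparator once, for events, in the cost-effectiveness paragraph. The one controlled KCCQ result in the protocol is from the randomized in-hospital trial described in the Introduction, where the "placebo-adjusted mean difference at 90 days was 4.5 points favouring empagliflozin".

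**The concern.** Entry requires dyspnoea with two signs of congestion, a raised natriuretic peptide and i.v. loop diuretic treatment. The baseline for KCCQ-TSS and 6MWD falls in that same admission. Over the next 90 days a treated patient's score can rise through recovery from the episode, through usual care, or through the drug. A change score in the treated group alone is the sum of these and cannot separate them.

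The endpoint text names no contrast that would do so. The responder endpoint is worded as improvement after 90 days of treatment, which literally fits only patients who take the drug. A report that follows the text could present a mean gain and a responder rate for the treated group under an efficacy aim, with nothing to show how much would have occurred without the drug.

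**Working it through.** The protocol gives no expected change, SD, error rate, power or sample-size derivation, so there is no planned figure to reproduce. The calculation below only illustrates the mechanism.

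**Inputs**
- Responder threshold: 10 points (Study Endpoints).
- Drug effect: 0 or 4.5 points (4.5 from the Introduction).
- Mean recovery without drug, m: 0 to 30 points. Assumption.
- SD of the 90-day change: 15 to 25 points, normal distribution. Assumption.

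**Responder rate.** P(change ≥ 10) = 1 − Φ((10 − m − d)/SD), with d the drug effect. Example at SD 20 and m = 20: without drug, 1 − Φ(−10/20) = 69.1%; with 4.5 points, 1 − Φ(−14.5/20) = 76.6%.

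Each cell gives the rate without drug → with 4.5 points:

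| Assumed recovery | SD 15 | SD 20 | SD 25 |
|---|---|---|---|
| 0 | 25.2% → 35.7% | 30.9% → 39.2% | 34.5% → 41.3% |
| 5 | 36.9% → 48.7% | 40.1% → 49.0% | 42.1% → 49.2% |
| 10 | 50.0% → 61.8% | 50.0% → 58.9% | 50.0% → 57.1% |
| 20 | 74.8% → 83.3% | 69.1% → 76.6% | 65.5% → 71.9% |
| 30 | 90.9% → 94.9% | 84.1% → 89.0% | 78.8% → 83.6% |

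For recovery of 10 to 30 points, the 4.5-point effect adds 4.0 to 11.8 percentage points. The 50% at 10 points of recovery is built in, because the assumed mean then equals the threshold.

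**Share of the mean change due to drug.** 4.5/(4.5 + m) is 31% at m = 10, 18% at m = 20 and 13% at m = 30.

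**Within-group test with an inert drug.** The protocol does not announce such a test; this shows what one would do. The probability of p < 0.05 is Φ(m√n/SD − 1.96) + Φ(−m√n/SD − 1.96). With n = 100 and m = 5 it is 92%, 71% and 52% at SD 15, 20 and 25. With m = 10 or more it is at least 98%. With no recovery it is 5%.

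**Contrast with the registry.** Recovery common to both groups cancels in a treated-minus-registry difference. For 4.5 points, 80% power and two-sided 0.05, n per group = 2(SD/4.5)²(1.96 + 0.84)², which gives 175, 311 or 485 at SD 15, 20 or 25. At SD 20, power is 20% with 50 per group and 36% with 100 per group. These group sizes are assumptions, as the protocol does not say how large the registry will be.

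The documents give no effect size or SD for 6MWD, so the argument applies to it without a number.

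**The case against.** A reader might infer that natural recovery alone *will* pass for efficacy, and would do so even if patients who accept and decline the drug were alike. The documents do not support that. The registry has the same KCCQ-TSS and 6MWD assessments, and if the groups were alike, shared recovery would cancel in the contrast between them. The problem is that the endpoints are not tied to this contrast.

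Other objections also stand:

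- An in-hospital baseline is not in itself a flaw. The randomized trial in the Introduction also started treatment after in-hospital stabilization, and reported KCCQ against placebo.
- The stabilization criteria mean that some early recovery precedes baseline.
- Nothing shows that patients will be on newly started HF therapy by day 90. The Introduction says that such therapy may be delayed while echocardiography is awaited.
- That 4.5 is below 10 does not show the threshold to be wrong: one is a difference between group means, the other a cut-off for an individual.
- The table does not show what share of responders would have responded anyway. That needs the further assumption that the drug turns no responder into a non-responder.

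The strongest reply is that change from baseline only defines a variable, that the protocol never says within-group change will be offered as evidence of efficacy, and that the contrast may be left to an analysis plan. Models and covariates can be left there. Which group an efficacy endpoint is compared with, in a non-randomized study, is a design decision. The protocol has made it for events and not for these measures.

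**Conclusion.** The point holds as a matter of how the endpoints are fixed. Followed as written, the KCCQ-TSS and 6MWD endpoints give an uncontrolled change that can look favourable with an inert drug.

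Its size cannot be taken from the documents. At SD 20 the no-drug responder rate runs from 31% to 84% over assumed recovery of 0 to 30 points, so a high rate is possible but not established. What is more stable is that a 4.5-point effect moves the rate by about 4 to 12 percentage points, which the treated group's rate alone cannot reveal.

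Mortality and the HF-event components have no baseline value and are not affected by this mechanism. The point therefore does not reach the whole efficacy aim.

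**What to change.** In Study Endpoints and Statistical analysis:

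1. State that change within the treated group and the 10-point responder rate are descriptive and are not evidence of efficacy.
2. For KCCQ-TSS and 6MWD, including KCCQ-TSS where it enters the primary composite, make the efficacy comparison the day-90 treated-minus-registry difference. Adjust it for the patient's own baseline value, days from admission to the baseline assessment, and the baseline confounders already collected under Table 1 (comorbidities, medications, natriuretic peptide, eGFR).
3. Limit the efficacy wording for these components to a non-randomized comparison.
4. State as limitations that patients who decline the drug are a selected group, and that KCCQ-TSS and 6MWD are open to reporting and effort bias when treatment is known. The registry contrast removes neither.

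The cost is protocol wording and one adjusted analysis on assessments already scheduled for both groups. The price is a weaker and less precise claim: about 20% power for 4.5 points with an assumed 50 per group and SD 20, before any gain in precision from baseline adjustment.

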Secondary Outcomes	
 
• Change from baseline in KCCQ-TSS after 90 days of treatment.
 
• Change from baseline in log-transformed NT-proBNP level over 90 days of treatment.
 
• Change in NYHA class
 
• Days alive and out of hospital from study drug initiation until 90 days after initial hospital discharge.
 
• Days alive and out of hospital from study drug initiation until 90 days after randomization.
 
• Time to first occurrence of cardiovascular death or heart failure event until end of trial visit.
 
• Occurrence of HHF until 90 days after initial hospital discharge.
 
• Occurrence of chronic dialysis or renal transplant or sustained reduction of <math>\geq 40\%</math> eGFR, or 
 
- Sustained eGFR <math>< 15\text{mL/min}/1.73\text{m}^2</math> for patients with baseline eGFR <math>\geq 30\text{ mL/min}/1.73\text{m}^2</math>
 
- Sustained eGFR <math>< 10\text{mL/min}/1.73\text{m}^2</math> for patients with baseline eGFR <math>< 30\text{ mL/min}/1.73\text{m}^2</math>.
 
 
 
• Weight loss per mean daily loop diuretic dose after 15, 30, 60 and 90 days of treatment.
 
• Change from baseline in 6MWD at 90 days.
 
• Cost effectiveness of early initiation of empagliflozin for heart failure events avoided and quality-of-life years (QALY) gained.
 

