**Exclusion criteria:**

1. Cardiogenic shock
2. Documented history of HF with previous HF admission
2. Current hospitalization for acute HF primarily triggered by pulmonary embolism, cerebrovascular accident, or acute MI
3. Interventions in the past 30 days prior or planned during the study:
  - Major cardiac surgery, or TAVI, or PCI, or MitraClip
  - Implantation of cardiac resynchronization therapy device
  - Cardiac mechanical support implantation
4. Current or expected heart transplant, LVAD, IABP, or patients with planned inotropic support in an outpatient setting
5. Haemodynamically severe uncorrected primary cardiac valvular disease planned for surgery or intervention during the course of the study
6. eGFR  $< 20$  mL/min/1.73m^2 as measured during index hospitalization (latest measurement before randomization) or patients requiring dialysis
7. Type 1 diabetes mellitus
8. History of ketoacidosis, including diabetic ketoacidosis
9. Current or prior treatment with SGLT2 inhibitors in the 90 days prior to enrolment.

**Study locations:** This study will be primarily conducted at The Chinese University of Hong Kong/ Prince of Wales Hospital.

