### **5. ETHICS**

This clinical investigation will be conducted in accordance with this Clinical Investigation Plan. The application for research ethics will be submitted to the Joint CUHK-NTEC Clinical Research Ethics Committee. This study will be conducted in accordance with the principles of the Declaration of Helsinki.

Study drug will be provided by the study team (free of charge to the patient) as an open-label treatment for 90 days.

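### The stated cost basis for the ICER covers hospital admissions and visits but not empagliflozin, so as written it understates the cost of early initiation and can show a saving that counting the drug would remove.

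*Protocol*

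**What the plan says.** The Protocol Summary lists as a secondary outcome "Cost effectiveness of early initiation of empagliflozin for heart failure events avoided" and for QALYs gained. The Statistical analysis paragraph of Section 2 promises an ICER on both scales, takes the events of registry patients as the reference, and then states the cost basis: "Costs will be based on Hospital Authority gazette prices for hospital admissions and visits". This is the only costing rule in the Protocol.

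The drug itself is free to the patient. Section 5 (Ethics) says: "Study drug will be provided by the study team (free of charge to the patient) as an open-label treatment for 90 days". The Study procedure paragraph adds that the research pharmacy dispenses it.

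The comparator is made up of those that "meet inclusion and none of the exclusion criteria but declined study medication will be invited to be followed-up in a registry as reference group". They have the same baseline and follow-up assessments as treated patients, without the study drug. Exclusion 9 applies to them too: "Current or prior treatment with SGLT2 inhibitors in the 90 days prior to enrolment". Other treatment is left open: "Patients should receive usual care per current relevant local and regional guidelines, as defined by their clinicians".

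Table 1 collects clinical events (deaths, A&E visits for acute heart failure, "unplanned outpatient clinic visit, re-admission for heart failure") and, at every visit, SGLT2 inhibitor prescription records. Nothing links those records to a price. The Introduction names cost as a major obstacle to starting this drug class early.

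**The concern.** The numerator of an ICER is the difference in total relevant cost between two strategies. Here the strategies differ by design in one resource, the drug, and the stated cost basis does not name it. Nor would the drug enter by another route: it comes free from the study team, so it would not be part of the price of an A&E visit, a clinic visit or a re-admission.

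What is at stake is the cost-effectiveness outcome alone. If price-weighted event cost is lower in the treated group, the rule as written reports a saving, and the price of the drug never enters. A reader could take that as evidence against the cost obstacle that the Protocol itself raises. The efficacy and safety endpoints are not affected.

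**Working it through.** The Protocol gives no ICER, unit price or cost total, so there is no figure to reproduce. The check is algebra, followed by an illustration.

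**1. The rule as written and with the drug counted**

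Let *k* index event types, with price p_k and events per patient r_k in the treated (T) and registry (R) groups. Let *c* be the daily price of an SGLT2 inhibitor and *d* the mean days supplied per patient.

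- As written: ΔW = Σ p_k (r_k,T − r_k,R)
- With the drug: ΔF = ΔW + c (d_T − d_R)

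The omitted amount is c (d_T − d_R). It is positive whenever treated patients receive more drug-days than registry patients. Exclusion 9 puts both groups off the drug class at entry, and registry patients have declined the study drug, so only new usual-care prescriptions during follow-up can offset it.

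**2. Inputs for an illustration**

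- Heart failure events of 10.6% on drug and 14.7% on placebo, in a trial of 530 patients randomised 1:1, hence 265 per arm (Introduction).
- Assumption: these percentages are read as events per patient.
- Assumption: the event mix is the same in both groups, so that one mean event price *P* applies.
- Assumption: the full 90 days are supplied to treated patients.
- Assumption: registry patients spend a share *u* of follow-up days on an SGLT2 inhibitor, with *u* = 0, 0.25 or 0.50. The Protocol gives no value.
- *P* and *c* are not in the Protocol. Results are given as a share of *P*, then over an assumed range.

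**3. Event difference**

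- Difference: 0.147 − 0.106 = 0.041 events avoided per patient
- SE = √(0.106 × 0.894/265 + 0.147 × 0.853/265) = 0.0288
- Approximate 95% interval: 0.041 ± 1.96 × 0.0288, or −0.015 to 0.097

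**4. Break-even**

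ΔW = −0.041 P for every value of *c*. ΔF = 90(1 − u)c − 0.041 P. The sign turns from saving to added cost once the net 90-day drug cost exceeds 0.041 P, which is 4.1% of the mean event price (9.7% at the upper limit of the interval).

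| *u* | Net drug-days per patient | Unpriced drug-days per event avoided | Break-even daily price, share of *P* |
|---|---|---|---|
| 0 | 90 | 90/0.041 = 2,195 | 0.041/90 = 0.046% |
| 0.25 | 67.5 | 67.5/0.041 = 1,646 | 0.041/67.5 = 0.061% |
| 0.50 | 45 | 45/0.041 = 1,098 | 0.041/45 = 0.091% |

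At *u* = 0, the break-even daily price is 2.3 for *P* = 5,000, 4.6 for 10,000, 11.4 for 25,000 and 22.8 for 50,000 (assumed currency units).

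**5. One worked case**

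Assume *P* = 10,000, *c* = 10 and *u* = 0.

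- As written: −0.041 × 10,000 = −410 per patient, a saving
- With the drug: 90 × 10 − 410 = +490 per patient, or 490/0.041 ≈ 11,950 per event avoided

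The reverse also occurs in the assumed range. With *P* = 50,000 and *c* = 10, counting the drug gives 900 − 2,050 = −1,150, which is still a saving. The omission always moves the cost in one direction, but whether it changes the sign depends on prices that the Protocol does not give.

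**The case against.** The strongest reply is that this is a gap and not a rule. The sentence says what costs are based on; it does not say that nothing else will be costed. It directly follows the statement about registry events, so it can be read as the price source for those events. Unit prices and their sources are often left to an economic plan, and the prescription records in Table 1 suggest that drug use was meant to count.

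Part of this stands. The wording is not expressly exclusive, and a reader who infers that the Protocol forbids costing the drug goes further than the text. But the Protocol is not silent on costs either. It names the cost components and leaves out the one that differs between the groups by design. A later plan that added the drug would be extending this rule.

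A reader might also infer that the cost-effectiveness question can no longer be answered. The Protocol does not support that: daily dosing and the 90-day supply are stated and prescriptions are recorded, so drug cost can be added at analysis with one unit price.

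Nor does it follow that a false saving will appear. The illustrative rates come from another, randomised trial in which about one-third had new-onset heart failure. Here the comparator is patients who declined the drug, and the event-difference interval includes zero. At a difference of zero or below, with an equal event mix, the rule shows no saving and only understates cost. If the mix differs, a shift from admissions to clinic visits could show a saving with no fall in events. No figure was worked out for the QALY ratio; it shares the same numerator.

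Self-selection of the registry patients is a separate matter and adds no weight here.

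**Conclusion.** The point holds in this form: the only cost basis that the Protocol states for the ICER leaves out the cost of the intervention. Followed as written, it understates the incremental cost of early initiation by the net drug-days times the daily price, and it can show a saving where counting the drug would show a net cost. This rests on reading the sentence as it stands and on treated patients receiving more SGLT2 inhibitor than registry patients.

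The actual size is unknown. The 4.1% break-even is an illustration that depends on borrowed rates read as events per patient and on an equal event mix. The point should be fixed, but it concerns one secondary outcome, and that outcome remains answerable once the rule is corrected.

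**What to change.** Change the cost sentence in the Statistical analysis paragraph so that it covers *hospital admissions, visits and SGLT2 inhibitor acquisition (unit price × days supplied)*. State that this applies alike to treated and registry patients, that days supplied come from research-pharmacy dispensing and the Table 1 prescription records, and that the drug is costed despite free supply in the study. Name the price source. A break-even price and a price sensitivity range would help readers but are optional.

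The cost is a short change to the text and no new data collection. The downside is a less favourable ICER and a price source to choose and defend.
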